#### HOOS Jr. Score at 6 weeks, 3 months, 6 months, 1 year and 2 years

HOOS Jr. Score are assessed at the Pre-Op visit and at 6 weeks, 3 months, 6 months, 1 year and 2 years. Results within each visit window will be summarized and changes from baseline will be provided using the Per Protocol Analysis Set. Standard continuous summaries will be supplemented with 95% confidence intervals.

#### Forgotten Joint Score (FJS-12)

FJS-12 are assessed at the 6 week visit and at 3 months, 6 months, 1 year and 2 years. Results within each visit window will be summarized and changes from baseline will be provided using the Per Protocol Analysis Set. Standard continuous summaries will be supplemented with 95% confidence intervals.

### **9.12.3 Exploratory Endpoint Analysis**

Exploratory analyses will include the following:

- Correlation of functional and health status outcomes (Harris Hip Score, HOOS Jr, and FJS-12) vs. RSA observations may be explored.

### **9.13 Safety Endpoint Analysis**

Adverse Events will be coded according to the Medical Dictionary for Regulatory Activities (MedDRA) version 21.1. Analyses will be conducted for all subjects in the Safety Analysis Set.

An overall summary of the AE incidence within each surgical approach group will be presented and will include the number and percentage of subjects having one or more:

- Serious adverse event (SAE)
- Device related AEs
- Procedure related AEs
- Withdrawals due to AE
- Deaths

The number (%) of subjects with adverse events will be presented by MedDRA system organ class (SOC) and preferred term (PT) for all device related AEs, procedure related AEs and SAEs. A subject-level listing will be provided to display details of all reported AEs.

### **9.14 Plans for Interim Analysis**

There are no formal interim analyses that are designed to potentially stop or change the study design. A planned interim summary analysis will take place after all subjects have completed the 1 year visit in order to give product development an understanding of acetabular cup subsidence that might be expected for future product development purposes. There is no intention to utilize this interim analysis as a means to justify stopping the study early.

### **9.15 Handling of Missing Data**

Only subject data which is collected in the study will be utilized in analyses; there will be no imputation of missing data.

## **10 STUDY MANAGEMENT AND ADMINISTRATION**

### **10.1 Investigator Responsibilities**

In conducting this clinical study, the Investigator is responsible for:

- Ensuring that the clinical study is conducted according to the Declaration of Helsinki, applicable local regulations, the clinical study agreement and the protocol;
- Protecting the rights, safety and welfare of subjects under the Investigator's care; and
- Ensuring the integrity of the data.

Prior to the initiation of this clinical study at each site, the responsible Principal Investigator will approve this protocol by signing the signature page. This signature confirms that the clinical study will be performed in compliance with the protocol.

## **10.2 Good Clinical Practice**

The study will be conducted in accordance with the GCP and the appropriate regulatory requirement(s). The Investigator will be thoroughly familiar with the appropriate use of the study device as described in the Instructions for Use. Essential clinical documents will be maintained to demonstrate the validity of the study and the integrity of the data collected. Master files should be established at the beginning of the study, maintained for the duration of the study and retained according to the appropriate regulations.

## **10.3 Ethical Considerations**

The study will be conducted in accordance with ethical principles founded in the Declaration of Helsinki. The REB will review all appropriate study documentation in order to safeguard the rights, safety, and well-being of the subjects. The study will only be conducted at sites where initial and annual REB approval has been obtained. In addition, a copy of the REB approval letter must be filed on site in the Investigator's study files.

The protocol, Instructions for Use, informed consent form, advertisements (if applicable), written information given to the subjects, safety updates, annual progress reports, and any revisions to these documents will be provided to the REB by the Investigator. When applicable, amendments to the protocol will be submitted for REB review before implementation.

## **10.4 Subject Information and Informed Consent**

After the study has been fully explained, written informed consent will be obtained from either the subject or his/her guardian or legal representative prior to study participation. The method of obtaining and documenting the informed consent and the contents of the consent will comply with GCP and all applicable regulatory requirement(s), which at a minimum include:

- The most current, approved ICF is completed by the subject prior to the start of study specific procedures;
- The subject personally signed and dated the ICF;
- The investigator or designated study personnel has also signed and dated the ICF;
- The subject's source describes the consent process, including date, by whom, that the subject had an opportunity to ask questions, and that they were offered a copy of their signed ICF; and
- The signed ICF(s) are retained by the investigator and are available for inspection.

## **10.5 Subject Confidentiality**

In order to maintain subject privacy, all eCRFs, study device accountability records, study reports and communications will identify the subject by the assigned subject number. The Investigator will grant monitor(s) and auditor(s) from the Sponsor or its designee and regulatory authority(ies) access to the subject's original medical records for verification of data gathered on the eCRFs and to audit

the data collection process. The subject's confidentiality will be maintained and will not be made publicly available to the extent permitted by the applicable laws and regulations.

## **10.6 Direct Access to Source Data**

The study will be monitored by DePuy Synthes or its designee. Monitoring will be done by personal visits from a representative of DePuy Synthes (site monitor) and will include on-site review of the eCRFs for completeness and clarity, cross-checking with source documents, and clarification of administrative matters will be performed. The review of medical records will be performed in a manner to ensure that subject confidentiality is maintained.

The site monitor will ensure that the investigation is conducted according to protocol design and regulatory requirements by frequent communications (letter, telephone, e-mail and/or fax).

Regulatory authorities, the REB, and/or DePuy Synthes quality assurance group may request access to all source documents, eCRFs and other study documentation for on-site audit or inspection.

Direct access to these documents must be guaranteed by the Investigator, who must provide support at all times for these activities.

## **10.7 Case Report Form Completion**

An electronic data capture system, compliant to 21 CFR Part 11, will be used to collect data from this study.

eCRFs will be completed for each study subject. It is the Investigator's responsibility to ensure the accuracy, completeness, and timeliness of the data reported in the subject's eCRF. Source documentation supporting the eCRF data should indicate the subject's participation in the study and should document the dates and details of study procedures, adverse events, and subject status.

The Investigator, or designated representative, should complete the eCRF pages as soon as possible after information is collected, preferably on the same day that a study subject is seen for an examination, treatment, or any other study procedure. Any outstanding entries must be completed immediately after the final examination. An explanation should be given for all missing data.

## **10.8 Record Retention**

The Investigator will maintain all study records according to GCP and applicable regulatory requirement(s). Records will be retained for at least 2 years after the completion of the clinical study, according to site procedures or according to applicable regulatory requirement(s) (whichever is longest). If the Investigator withdraws from the responsibility of keeping the study records, custody must be transferred to a person willing to accept the responsibility. The Sponsor must be notified in writing if a custodial change occurs.

Study documentation includes, but is not limited to, the following:

- Source data, informed consents and enrollment logs
- Correspondence with the REB, DePuy Synthes, the site monitor, or other Investigators
- Study protocol and any amendments issued
- Protocol and Informed Consent approvals from the REB

## **10.9 Investigator agreements and curricula vitae of Investigator(s), and the Site Signature and Delegation Log Investigator Reports**

The Investigator(s) is required to complete the following reports:

1. Withdrawal of REB Approval – Notification must be sent to the Sponsor within 5 working days
2. Informed Consent – A report of any use of the investigational device without a signed Informed Consent form must be forwarded to the Sponsor and the REB within 5 working days of the occurrence
3. Investigational Plan Deviations – Emergent deviations must be forwarded to the REB and the Sponsor as soon as possible and within 5 working days of the event. Any departures from the protocol must be fully documented in the eCRF and source documentation
4. Progress Reports – Annual progress reports must be forwarded to the REB and the Sponsor
5. Final Report – A final report/closure submission must be filed with the REB and the Sponsor within 3 months of the Investigator's completion of study site closure.
6. Principal Investigator(s) may delegate a qualified associate(s) to complete one or more of the above functions. However, the Principal Investigator retains the overall responsibility for subject safety, proper conduct of the study including obtaining subject consent, compliance with this study plan, and the collection of all required data.

## **11 SPONSOR OBLIGATIONS**

### **11.1 Investigator(s) Training**

DePuy Synthes will select only Investigator(s) with extensive experience in THA. The protocol will be reviewed with the Investigator(s) and their study personnel at the Site Initiation Visit. Furthermore, they will be instructed on how to complete the study documentation.

### **11.2 Study Monitoring**

Study monitoring will be carried out in compliance with FDA regulations (21CFR 812) and all GCP guidelines and will be consistent with the sponsor's internal monitoring procedures.

## **12 RESEARCH ETHICS BOARDS AND REGULATORY REQUIREMENTS**

### **12.1 REBs**

The protocol, informed consent form and other applicable study-related documents must be submitted to the appropriate REB and written approval must be obtained and submitted to DePuy Synthes prior to enrolling any subjects.

The Investigator will promptly report to the REB any change in the designation of Principal Investigator role and all unanticipated problems involving risks to human subjects and will not make any changes in the research plan without REB approval, except when necessary to eliminate immediate hazards to human subjects. Those amendments involving significant risk or change require REB approval and written documentation of this approval must be submitted to the DePuy Synthes.

The Investigator must report to the REB at least yearly on the progress of the investigation. A letter from the REB should document continuing REB review. Notification to the REB by the Investigator within 3 months after completion, termination, or discontinuation of the study at the specific site must be documented.

Other Investigator responsibilities to the REB and DePuy Synthes include the following:

- During the conduct of the study, submit progress reports to the REB and Sponsor as required (Note: the annual progress report to the REB will fulfill the Investigator's responsibility to submit progress reports to the Sponsor).
- As required, obtain approval from the REB for protocol amendments and for revisions to the informed consent or subject recruitment advertisements.
- Provide REB with any other information it requests before or during the conduct of the study.
- Maintain a file of study-related information that includes all correspondence with the REB and Sponsor.
- Notify REB within 3 months after study completion, termination or discontinuation.
- Notify DePuy Synthes, within 5 working days, of withdrawal of approval by the reviewing REB.

## **12.2 Protocol Amendments**

As appropriate, DePuy Synthes will submit changes in the protocol to the investigators, the appropriate regulatory authorities and REBs. REB approval is required for all substantial amendments prior to implementation of any changes to study procedures.

An amendment is regarded substantial when they are likely to have a significant impact on:

- The safety or physical or mental integrity of the subjects;
- Scientific value of the trial;
- Conduct or management of the trial;
- Quality or safety of an investigational medical product used in the trial.

## **12.3 Protocol Deviations**

A protocol deviation is defined as a divergence from a specific element of a protocol (e.g., missed test or procedure, visit out of window, non-adherence to inclusion/exclusion criteria).

Investigators may not deviate from the protocol except where necessary to protect the life or physical well-being of a subject in an emergency.

Deviations shall be reported to DePuy Synthes regardless of whether medically justifiable or taken to protect the subject in an emergency. Subject specific deviations will be reported in the eCRFs. Investigators will also adhere to procedures for reporting study deviations to their REB in accordance with their specific REB reporting policies and procedures. Regulations require that Investigators maintain accurate, complete and current records, including documents showing the dates and reasons for each deviation from the protocol.

## **13 PUBLICATION POLICY**

At the conclusion of the study, a multicenter manuscript will be prepared for publication in a reputable scientific journal. The publication of the principal results from any single-site experience within the study is not allowed until the preparation and publication of the multi-center results. Exceptions to this rule require the prior approval of DePuy Synthes. The analysis of other pre-specified and non-pre-specified endpoints will be performed by Data Management. Such secondary analyses, as well as other proposed investigations, will require the approval of DePuy Synthes. For purposes of timely abstract presentation and publication, secondary publications will be delegated to the appropriate principal authors, and final analyses and manuscript review for all multi-center data will require the approval of DePuy Synthes.

## 14 Appendix A

### Part Codes

#### Sector Gription Acetabular Shell

Gription	
Code	Size (mm)
1217-32-048	48
1217-32-050	50
1217-32-052	52
1217-32-054	54
1217-32-056	56
1217-32-058	58
1217-32-060	60
1217-32-062	62
1217-32-064	64
1217-32-066	66

3L92509	9	3L92499	9	L20309	9	L971109	9	3L93709	9
3L92510	10	3L92500	10	L20310	10	L971110	10	3L93710	10
3L92511	11	3L92501	11	L20311	11	L971111	11	3L93711	11
3L92512	12	3L92502	12	L20312	12	L971112	12	3L93712	12
3L92513	13	3L92503	13	L20313	13	L971113	13	3L93713	13
3L92514	14	3L92504	14	L20314	14	L971114	14	3L93714	14
3L92515	15	3L92505	15	L20315	15	L971115	15	3L93715	15
3L92516	16	3L92506	16	L20316	16	L971116	16	3L93716	16
3L92518	18	3L92508	18	L20318	18	L971118	18	3L93718	18
		3L92521	20	L20320	20	L971120	20		

125° Standard Offset Collarless		125° Standard Offset Collared		135° Short Neck Collarless		135° Short Neck Collared	
Code	Size	Code	Size	Code	Size	Code	Size
L981208	8	L971208	8	L981308	8	L971308	8
L981209	9	L971209	9	L981309	9	L971309	9
L981210	10	L971210	10	L981310	10	L971310	10

## 15 Appendix B

### Anticipated Adverse Events

In addition to the information provided in the Instructions for Use, included with the packaging for all implants, the following surgical adverse events are anticipated. **Assuming the following events are consistent with the normal postoperative course, then they do not have to be reported as Adverse Events.**

UP TO 24 HOURS POSTOPERATIVE	
Genitourinary	

Urinary retention

Cardiovascular	

Hypotension, not requiring treatment

Hypertension, not requiring treatment

Dysrhythmia (resolving within 36 hours post-op)

Central Nervous System	

Incisional pain

Post-op consequences of narcotics use

Fatigue

Integumentary	

Venous congestion without thrombosis (foot swelling alleviated with lower limb is raised)

PRIOR TO DISCHARGE	
Hematological	

Changes in lab values not resulting in clinical symptomatology (Electrolytes, CBC, BS, PT/PTT)

Anemia, not requiring treatment

Gastrointestinal	

Transitory:

Nausea

Vomiting

Constipation

Diarrhea

Central Nervous System	

Headache

Disorientation

Confusion

Dizziness

Incision/operative site pain

Respiratory	

Atelectasis, not requiring treatment

Integumentary	

Foot swelling, not requiring intervention

Surgical site ecchymosis

Sanguineous/serosanguinous drainage from incision

Skin blisters secondary to tape/adhesive

Suture granuloma not involving cellulitis or deeper infection ('spitting suture', abscess suture)

Constitutional	

Elevated temperature (no greater than 101°F)

If you have any questions about potential adverse events (or reporting), please contact DePuy Synthes Clinical Research.

## Revision History

Revision Number	Revision Date (DD/MMM/YYYY)	Reasons for Revision
Version 1	28/JUN/2021	Initial Version

## 1 Study Design

This study is designed as a prospective, multi-center, non-randomized, non-controlled study. This study does not limit the procedures involved in the treatment of the subject as long as the protocol specified products are utilized.

### 1.1 Study Objectives

#### 1.1.1 Primary Objective

The primary objective is to establish the mean superior cup migration of the Pinnacle Acetabular Shell using model-based RSA over the first two years post-implantation. The primary endpoint is the mean vertical subsidence (Y translation, also known as superior cup migration) at 2 years as measured with RSA. This will be summarized for each surgical approach separately, as well as combined.

#### 1.1.2 Secondary Objectives

The secondary objectives are:

- To establish the subsidence profile of the Pinnacle Acetabular Shell; this will be accomplished by determining the mean subsidence at 3 months, 6 months and 1 year as measured with RSA.
- Other RSA measurements (X and Z translations in mm, X, Y, and Z rotations in degrees, and maximal total point motion in mm) at all time points.
- Functional and health status will be measured with Harris Hip Score, HOOS Jr. and Forgotten Joint Score (FJS-12).
- Analysis of cup positioning (inclination and version)
- Linear head penetration: Linear head penetration (in mm) will be performed by examining the change in distance between the center of the femoral head and the center of the acetabular shell between the 6-week (baseline) exam and the 3 months, 6 months, 1 year and 2 year exam. The femoral head center is determined

by fitting a CAD sphere to the articular region of the femoral head (ignoring the trunnion area). The acetabular shell center is determined in a similar manner but also uses the silhouette of the cup face to determine its' centerpoint.

### 1.1.3 Exploratory Objectives

The following will be summarized as exploratory analyses:

- Subsidence for subset of subjects where RSA data was obtained prior to discharge
- Analyses to examine the correlation of functional and health status outcomes vs. RSA observations may be explored.

## 2 Interval Windows

The study includes the following periods: Pre-op, Operative, Prior to Discharge, 6 Weeks, 3 Months, 6 Months, 1 Year, 2 Years. Intervals related to each are shown in Table 3, below.

Table 3 Interval Windows for Non-Radiographic Study Visits

Visit	Minimum Day	Maximum Day	Midpoint Day
Pre-Op*	-90	0	
Operative	0	0	0
Prior to Discharge	1	Discharge	
6 Weeks	28	56	42
3 Months	60	120	90
6 Months	135	225	180
1 Year	275	455	365
2 Years	640	820	730

\* For radiographs Pre-Op study film window is from -270 days to DOS.

Time point specific data collected to satisfy the primary and secondary efficacy-related objectives will be assessed for compliance with these intervals. Only data which can be attributed to the visit intervals in Table 3 will be used in the analysis of primary and secondary endpoints. This visit will be hereafter referred to as the Analysis Visit and the originally recorded visit as the Nominal Visit. If multiple measurements fall into the pre-

operative window, or into the ‘Prior to Discharge’ post-operative window, the result collected most proximate to surgery will be utilized. For all post-operative visits after the ‘Prior to Discharge’ visit, if multiple measurements fall into the window then the last value within the window will be utilized for analysis.

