### **4 Analysis Sets**

The following analysis sets are defined:

- **All Enrolled** – Subjects will be considered enrolled if they have consented and authorized release of their personal health information.
- **Safety** – The Safety Analysis Set consists of all enrolled subjects who receive THA surgery. Subjects will be analyzed according to the surgical approach applied during of the study.
- **Per Protocol** – The Per Protocol (PP) Analysis Set will be a subset of Safety Set subjects who have no major inclusion/exclusion protocol violations, and who have a 6 weeks RSA exam and at least one post-baseline RSA exam. Subjects will be analyzed according to the actual treatment (surgical approach) received during of the study.

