### 6.2 Disposition of Study Subjects

Counts of the following categories of subjects by surgical approach and in total will be provided: All Enrolled dataset, Safety, major inclusion/exclusion protocol violations, Per Prototol, non inclusion/exclusion major protocol violations, deaths, withdrawals, study completion, ongoing in the study.

A subject accounting table using the Safety set will also be provided to account for the following at each follow-up interval:

- Treated: the count of subjects treated. This should not vary per visit;
- Not Yet Due: the count of subjects who do not have an evaluation at the visit and who, based on date of surgery and date of data extract, are not yet in-window for the visit;
- Theoretical Due: the count of subjects treated and not counted in Not Yet Due.
- Death: the count of theoretical subjects who died after the start of the window and who do not have data at the visit;
- Revision: the count of subject theoretically due, without data at the visit, who were revised. Revisions will be identified through consensus between Medical Affairs and the clinical study team using the data from the AE and study completion CRFs;
- Not Yet Overdue: count of theoretical subjects within the evaluation time window. Do not count subjects who have data at the visit or subjects who are counted in Death or Revision;
- Expected Due: the count of subjects theoretically due who are not counted in Death, Revision, Not Yet Overdue;
- Actual data on file (records with a date): the count of Expected subjects with a record with a date for each of the following endpoints: RSA measured subsidence, cup positioning (6 Weeks only), Harris Hip, HOOS Jr., Forgotten Joint Score, and Linear Head Penetration. A count of subjects with a record with a date in any of the listed endpoints will also be provided and a follow-up rate will be calculated using the number of Expected subjects in the interval as denominator;
- Scorable data: the count of Expected subjects with a record with a date and where the endpoint was scorable/non-missing for the following endpoints: RSA measured subsidence, cup positioning (6 Weeks only), Harris Hip, HOOS Jr., Forgotten Joint Score, and Linear Head Penetration. A count of subjects with a record with a date of all of the listed scorable endpoints will also be provided and a follow-up rate (complete data) will be calculated using the number of Expected subjects in the interval as denominator.

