## **6.6 Primary Endpoint and Associated Hypotheses**

### RSA Measured Subsidence at 2 years

The primary endpoint of RSA measured subsidence (Y translation from week 6 in mm, also known as superior cup migration) results in the 2-year visit window will be summarized on the subset of subjects in the Per Protocol Analysis Set (primary analysis) who have 6 week and 2 year data for the analysis. The analysis will also be conducted on the subset of subjects in the Safety Analysis Set (supportive analysis) who have 6 week and 2 year data for the analysis. Standard continuous summaries will be provided along with 95% confidence intervals. These summaries will be provided for each surgical approach, as well as combined.

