## **6.7 Secondary Endpoints**

### 6.7.1 RSA Measured Subsidence and maximal total point motion at 3 months, 6 months, 1 year, and 2 years

X, Y, and Z translations from week 6 in mm and A, Y, and Z rotations in degrees, and maximal total point motion in mm will be summarized at the 3 month, 6 month, 1 year, and 2 years visit windows using the Per Protocol Analysis Set and the Safety Set. Standard continuous summaries will be provided along with 95% confidence intervals. These summaries will be provided for each surgical approach, as well as combined.

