## **6.11 Handling of Missing Data**

Only subject data which is collected in the study will be utilized in analyses; there will be no imputation of missing data.

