## **6.13 Sensitivity Analyses**

No sensitivity analyses will be conducted.

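### Both planned 2-year means use only in-window 6-week/2-year RSA pairs, and no analysis described in the SAP compares lost with retained cups or bounds the effect of their loss

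*SAP*

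**What the plan says.** - **Window rule (SAP 2).** "Only data which can be attributed to the visit intervals in Table 3 will be used in the analysis of primary and secondary endpoints". The 6-week window is days 28 to 56 and the 2-year window is days 640 to 820. The table holding these windows is titled "Interval Windows for Non-Radiographic Study Visits". Protocol 1.1 and 9.4 give the same day ranges for the visits at which RSA is done.
- **Primary and supportive analyses (SAP 6.6, Protocol 9.12.1).** The primary analysis takes Per Protocol subjects who have both exams. The supportive one takes those in the "Safety Analysis Set (supportive analysis) who have 6 week and 2 year data for the analysis".
- **Per Protocol set (SAP 4).** Safety Set subjects "who have no major inclusion/exclusion protocol violations, and who have a 6 weeks RSA exam", plus at least one later RSA exam.
- **Earlier visits (SAP 6.7.1).** RSA results are "summarized at the 3 month, 6 month, 1 year, and 2 years visit windows using the Per Protocol Analysis Set and the Safety Set".
- **Missing data (SAP 6.11, 6.13).** "there will be no imputation of missing data", and "No sensitivity analyses will be conducted".
- **Accounting (SAP 6.2).** Counts per visit include "Revision: the count of subject theoretically due, without data at the visit, who were revised". Deaths and revisions are removed from the denominator of the follow-up rate.
- **Loss (Protocol 8.1, 8.2).** Revision, whatever the component, is a listed reason for leaving early. Losses after surgery are not replaced, except where COVID-19 prevented the 6-week visit.

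**The concern.** Protocol 2.2 wants this study to supply a reference value for judging future hip products. If some cups leave the 2-year analysis because they are loosening, the mean over the remaining pairs is lower than the mean over all implanted cups. Loss for unrelated reasons (death, withdrawal of consent, revision of stem, head or liner) need not shift it.

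The supportive Safety Set analysis might be taken as a check on this, but it carries the same pair restriction. A cup lost before an in-window 2-year exam still contributes to the 3-month, 6-month and 1-year summaries, but nothing carries that information to 2 years. Protocol 6.6 requires RSA at an out-of-window unscheduled visit only when the previous visit's in-window exam was missed. A cup that loosens after an in-window 1-year exam may therefore have no later RSA value at all. Because revised subjects leave the denominator, their loss does not lower the reported follow-up rate either.

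**Working it through.** **1. The plan's own figure.** Inputs from Protocol 9.8 and SAP 5: SD 0.2 mm, n = 30 per approach.
- Margin = 2 × 0.2/√30 = 0.073 mm, as stated. With a t quantile on 29 df it is 0.0747 mm.
- Combined, n = 90: 2 × 0.2/√90 = 0.042 mm.

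**2. What separates the two analysis sets.** A subject with a 6-week and a 2-year exam already has the 6-week exam and one later exam that the Per Protocol definition requires. Among subjects with the pair, only a major inclusion/exclusion violation can remove someone from Per Protocol. Comparing the two means therefore carries no information about missing exams.

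**3. Illustration of selective loss.** The documents give no loss rate and no migration values for lost cups, so the following are assumptions: normal values, SD 0.2 mm at 1 and 2 years, correlation ρ = 0.8, and the k highest 1-year migrators of 30 lacking a 2-year exam.

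Bias of the retained mean = −ρ × SD × S_k/(30 − k), where S_k is the sum of the expected k largest of 30 standard normal values (2.043, 1.616, 1.365).
- k = 1: −0.16 × 2.043/29 = −0.011 mm
- k = 2: −0.16 × 3.659/28 = −0.021 mm
- k = 3: −0.16 × 5.024/27 = −0.030 mm

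Simulation of 40,000 groups gives the same biases, with t-based 95% CI coverage of about 93%, 90% and 86%. The mean half-width is 0.071 to 0.072 mm, against 0.074 mm with no loss, so the interval itself shows nothing unusual.

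Over other correlations, for k = 1 to 3:
- ρ = 0.5: bias −0.007 to −0.019 mm, coverage 94% to 92%
- ρ = 0.9: bias −0.013 to −0.033 mm, coverage 93% to 82%

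If the same happened in all three approaches (a further assumption), the combined mean would carry the same bias against its 0.042 mm margin: 0.0113/0.0422 = 27%, 0.0211/0.0422 = 50%, 0.0298/0.0422 = 71%.

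**4. What a likelihood analysis can recover.** In the scenario of step 3, loss depends only on the observed 1-year value. A maximum-likelihood analysis of the 1-year and 2-year values then has bias of at most 0.0003 mm.

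Now take one lost cup in 30 with excess d at 2 years and e already visible at 1 year. The remaining bias is −(d − 0.8e)/30.
- d = 1.0 mm, e = 0.5 mm: −(1.0 − 0.4)/30 = −0.020 mm
- d = 1.0 mm, e = 0: −1.0/30 = −0.033 mm, the same as with no model

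A cup that loosens after its last exam is therefore not recovered, and only a subject listing would bring it to the reader's notice.

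**The case against.** A reader might infer that the plan is blind to selective loss. The documents do not support that. SAP 6.2 counts deaths, revisions and scorable RSA data at each visit. SAP 6.5 lists protocol deviations, which Protocol 12.3 defines to include missed tests and out-of-window visits. SAP 6.9 lists adverse events and counts those leading to withdrawal. The per-visit n and maximum would fall if a high 1-year migrator were absent at 2 years. These are real but indirect signals. None joins a subject's earlier migration to the reason for loss, or says how far the 2-year mean could move.

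A reader might also infer that the 2-year mean is biased low. That is not shown: the documents give neither the rate nor the direction of loss, and an exclusion criterion removes patients in whom the surgeon expects considerable migration. Nor do the gaps between windows measure discarded exams. The largest, days 456 to 639, is a period with no scheduled visit.

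Two further points stand. A revised cup has no 2-year migration in place, so a mean over cups still in place, with revisions counted separately, is a legitimate description. That is a reason to keep the planned summary as primary. The table shells (SAP 10) are in a separate file that was not available, and a subject-level RSA listing may already be there.

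Two replies carry less weight. SAP 6.14 allows post-hoc analyses, but an analysis named in advance is more convincing. Protocol 8.2 promises to include data already received on subjects who discontinue; for those without a 2-year exam, that can reach only the earlier visits.

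**Conclusion.** The point holds as a low-cost safeguard. The primary and supportive 2-year means share one complete-pair, in-window restriction, and the SAP text adds nothing that compares lost with retained cups or bounds the effect of losing them. Under the stated assumptions, losing the 1 to 3 highest 1-year migrators of 30 shifts an approach mean by about 0.01 to 0.03 mm, against a planned margin of 0.073 mm, and reduces coverage to about 93% to 86%. These sizes rest on an assumed loss pattern, the planning SD and an assumed correlation, none of which the documents can confirm for lost cups. The study is descriptive with exploratory intervals, so the effect is on the estimate and its coverage; no test or power is involved. The Table 3 title is a labelling slip: its windows govern the RSA endpoints.

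**What to change.** Keep the planned 2-year summary as primary and replace SAP 6.13 with two items.

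1. **A listing, by approach,** of every Safety Set subject without an in-window 6-week/2-year pair. Give the reason and, where a reference exam exists, the last Y translation and its day. Mark subjects with no reference exam as having no Y translation, because Protocol 6.7 defines it only relative to that exam.
2. **One supportive repeated-measures likelihood analysis** on the Safety Set of all available post-reference Y translations. Use one stated time scale, for example postoperative day with each subject's actual reference day entered so that migration is zero there. Report the postoperative day-730 mean and 95% CI by approach and combined.

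Amend the SAP 2 sentence so that the window restriction covers the primary and secondary summaries but not this supportive analysis. Use out-of-window exams only where they have been centrally read; Protocol 6.7 names results only for the scheduled visits. Correct the Table 3 title.

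**Cost:** SAP wording, one listing and one model, so a little more analysis work. The model assumes that loss depends only on observed migration, describes migration as if the cup had stayed in place, and recovers nothing for a cup that loosens after its last exam. The listing needs no missing-data assumption. It should be read beside the model and is the item to keep if only one is adopted.
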